#### 2.5.2 Statistical hypothesis, model, and method of analysis

The primary effectiveness objective of this study is to demonstrate superiority of each inclisiran arm compared to control in terms of the percentage change from baseline in LDL-C to Day 270 in adults with elevated LDL-C. The statistical hypotheses that will be tested for each inclisiran arm are as follows:

- $H_0$ : The difference between participants treated with inclisiran and control in the least squares mean percentage change from baseline to the Day 270 visit in LDL-C= 0
- $H_a$ : The difference between participants treated with inclisiran and control in the least squares mean percentage change from baseline to the Day 270 visit in LDL-C < 0

The primary objective will be achieved if null hypothesis  $(H_0)$  rejected at the one-sided significance level of 0.025.

The primary analysis will use an analysis of covariance (ANCOVA) model on the percent change in LDL-C from baseline to Day 270 to test the superiority of inclisiran over control after missing data imputation.

Due to probable heterogeneity of variances between treatment groups, ANCOVA model which assumes unequal variances for treatment group will be used. The model will include the fixed effects of treatment group with baseline LDL-C as a covariate.

Multiple imputation will be used to impute missing data using a washout model specified in Appendix 5.5.1. A total of 500 imputed datasets will be created. The ANCOVA model will be fitted to each imputed dataset, and results will be combined using Rubin's combination rules. The estimate and corresponding 2-sided 95% confidence intervals of mean difference between treatment groups will be calculated. p-value for hypothesis test for mean difference will also be provided. The FAS will be used for this analysis. The family-wise error rate for comparisons of the two inclisiran arms with the lipid-lowering background therapy plus behavioural support arm will be controlled using the Holm procedure.

#### 2.5.3 Handling of intercurrent events

The approach of accounting for intercurrent events is as follows:

| Intercurrent
events (ICEs)         | Strategy and justification of handling ICEs  | Missing value imputation  |
|---------------------------------------|--|---|
| Study
treatment
discontinuation | Here interest is in effect of
treatment regardless of treatment
discontinuations due to any
reasons other than intercurrent
event. This event will be handled
using a treatment policy
strategy. | The LDL-C data collected post
discontinuation of study treatment
will be included in the analysis. If
there is no off-treatment data
available, then missing data on Day
270 or after treatment
discontinuation will be imputed
using missing not at random
(MNAR) for inclisiran arms and
using missing at random (MAR) |

Primary estimand:

| Intercurrent
events (ICEs)           | Strategy and justification of handling ICEs   | Missing value imputation  |
|---|---|---|
|   |   | approach for placebo arm participants.  |
| Deviation in
background
treatment | Interest is in effect of treatment
regardless of substantial changes
to background therapy during
study treatment. This will be
handled with a treatment policy
strategy . | The LDL-C data collected after
deviation in background treatment
will be included in the analysis.
Missing values will be imputed in
same way as mentioned in Appendix
5.5.1 |
| Use of
prohibited
medications     | Interest is in effect of treatment
regardless of changes in
concomitant lipid lowering
medication during study treatment.
This will be handled with a
treatment policy strategy . | The LDL-C data collected after
deviation in background treatment
will be included in the analysis.
Missing values will be imputed in
same way as mentioned in Appendix
5.5.1 |

#### 2.5.4 Handling of missing values not related to intercurrent event

The point of care device is used to measure lipid profile data at each visit. Any undetectable calculated LDL-C data due to device sensitivity for a lipid parameter will be considered as missing for the primary analysis.

Undetectable data will be imputed separately as per Appendix 5.5.1 and used in a sensitivity analysis.

LDL-C data will be calculated using Friedwald's formula as mentioned below:

LDL-C = Total cholesterol - HDL - Triglycerides/2.2

Friedewald's formula valid only when Triglycerides < 4.52 mmol/L

Other missing data are expected to be intermittent missing data and will be assumed to be missing at random. The post-death missing values will be treated in same way as other missing data. Imputation details for data missing at random in the washout model has been provided in Appendix 5.5.1.

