#### 2.5.5 Sensitivity analyses

The following sensitivity analyses will be performed for the primary estimand, to assess the robustness of the estimation in the presence of deviations from the assumptions specified in the primary analysis on the FAS only:

| Novartis | Confidential | Page 18 of 37           |
|----------|--------------|-------------------------|
| SAP      |              | Study No. CKJX839A1GB01 |

• Linear mixed-effect model for repeated measures (MMRM) analysis without multiple imputation

Analyses using the MMRM will include fixed effects for treatment, visits, interaction between treatment and visits, baseline LDL-C and interaction between baseline LDL-C and visit. Day 90 and 270 will be included as visit. The Restricted Maximum Likelihood (REML) estimation approach will be used with covariance structure set as "Unstructured". If the model does not converge with unstructured covariance matrix, the compound symmetry covariance matrix will be used in the mixed model.

As a sensitivity analysis, the imputation algorithm will be changed from a regression approach to a multivariate normal model to include in the imputation information that is provided by undetectable LDL-C values. An LDL-C value is undetectable when either

are outside of the limit of detection. Based on the limit of detection and through Friedewald's formula, a range for an LDL-C value can be calculated. In this sensitivity analysis, the LDL-C range is considered in the imputation model. As for the primary analysis, undetectable LDL-C values for either study arm are imputed under a MAR assumption, missing values in the placebo arm are imputed under a MAR assumption, and missing data on Day 270 or after treatment discontinuation in the inclisiran arm are imputed using a wash-out model (i.e., using a jump-to-reference approach).

In the sensitivity analysis, imputed baseline values will be restricted to  $\ge 0.1$  to avoid imputed values close to zero which can lead to numerical instabilities in the analysis of percentage LDL-C change from baseline.

The imputation will be carriedout using in SAS/R as mentioned in Appendix 5.5.2.

The analysis will be carried out using ANCOVA procedure as mentioned in section 2.5.2.

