## 5.5 Statistical models

#### 5.5.1 Multiple Imputation Wash-out model

A multiple imputation washout model will be utilized for the primary efficacy analysis of the percentage change in LDL-C from baseline to Day 270 endpoint. The washout model can be thought of as a control-based PMM that will be used to explore the possibility of missing data being MNAR for subjects who discontinued the study early. For subjects who discontinued the study early, their missing values will be imputed under the assumption that their outcome would be similar to those in the control group with similar background characteristics. For subjects in the inclisiran groups only missing Day 270 values will be imputed.

For subjects whose LDL-C values are undetectable i.e., both baseline and post-baseline due to device sensitivity for a lipid parameter in inclisiran groups will be considered as missing and imputed under MAR assumption.

For subjects in the control group, their missing values over all visits after early termination as well as undetectable values including both baseline and post-baseline due to device sensitivity for a lipid parameter will be imputed based on the missing at random (MAR) assumption.

Multiple imputation will be used to account for uncertainty in the imputation process and results from the imputed datasets will be combined using Rubin's method. Further details are provided below.

For the control group the following variables will be included in a multiple imputation procedure (SAS PROC MI), this assumes missing data are MAR:

- Baseline value of efficacy measurement (continuous)
- Observed value of efficacy measurement at Day 90 (continuous)
- Observed value of efficacy measurement at Day 270 (continuous)

For the subjects in the inclisiran group who completed the doses and with intermittent missing as well as undetectable data, the following variables will be included in a multiple imputation procedure (SAS PROC MI), this assumes missing data are MAR:

- Baseline value of efficacy measurement (continuous)
- Observed value of efficacy measurement at Day 90 (continuous)
- Observed value of efficacy measurement at Day 270 from the inclisiran group (continuous)

For the subjects in the inclisiran groups and with missing data at Day 270 which does not includes undetectable data, the following variables will be included in a multiple imputation procedure (SAS PROC MI), this assumes missing data are MNAR:

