• Baseline value of efficacy measurement (continuous)

| Novartis | Confidential | Page 32 of 37           |
|----------|--------------|-------------------------|
| SAP      |              | Study No. CKJX839A1GB01 |

For each undetectable LDL-C value, a range is determined based on Friedewald's formula. Below table will provide example range calculation when

are distributed in different categories.

As a next step, the undetectable LDL-C values are baseline are imputed to create 500 complete sets of baseline LDL-C values. The imputation is performed by fitting a normal distribution to all available baseline LDL-C values including the LDL-C ranges. The imputed values are obtained by sampling from the posterior predictive distribution. As prior distribution for mean and the standard deviation a normal distribution (mean=0, sd=10) and a half-t-distribution (df=3, scale=2.5) are chosen.

To create 500 complete data sets of baseline and post-baseline LDL-C data sets, the following approach is performed for each of the 500 data sets with complete baseline LDL-C data.

- 1. Fit a Bayesian linear mixed model to all available post-baseline LDL-C data including the LDL-C ranges from Day 90 and Day 270.
  - a. The model includes study arm, visit, and baseline LDL-C as well as all interactions as fixed effects.
  - b. The model includes a normally distributed patient-specific random effect and a normally distributed residual error. The variance of the residual error differs by study arm and visit.

| Novartis | Confidential | Page 34 of 37           |
|----------|--------------|-------------------------|
| SAP      |              | Study No. CKJX839A1GB01 |

- 2. For the missing values or undetectable LDL-C values of patient *i* at visit *j* in study arm *k* that are imputed under the MAR assumption, the imputed value is drawn from the posterior predictive distribution of the outcome (i.e., LDL-C) of patient *i* at visit *j* in study arm *k*.
- 3. For the missing values of patient *i* at visit *j* in the inclisiran arm that are imputed under the jump-to-reference assumption, the imputed value is drawn from the posterior predictive distribution of the outcome (i.e., LDL-C) of patient *i* at visit *j* whereas the components (e.g., fixed effects and random effects) of the posterior predictive distribution that are associated with the inclisiran arm are replaced by the corresponding value from the placebo arm.

The above imputation will be carried out using R software.

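### The primary analysis imputes undetectable LDL-C, baseline included, as ordinary missing data with no stated bound, although the SAP can calculate a range for each such value

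*SAP*

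**What the plan says.** SAP 2.5.4 sets the primary rule: "Any undetectable calculated LDL-C data due to device sensitivity for a lipid parameter will be considered as missing for the primary analysis". Appendix 5.5.1 applies it. Undetectable values, baseline and post-baseline, that arise "due to device sensitivity for a lipid parameter in inclisiran groups will be considered as missing and imputed under MAR assumption". In the control group, MAR imputation likewise covers "undetectable values including both baseline and post-baseline due to device sensitivity". The listed imputation variables are LDL-C at baseline, Day 90 and Day 270.

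SAP 2.5.5 then says that, from the detection limit and Friedewald's formula, "a range for an LDL-C value can be calculated". To use that range in a sensitivity analysis, "the imputation algorithm will be changed from a regression approach to a multivariate normal model to include in the imputation information" which the undetectable values carry. The appendix text on this range-based method begins: "For each undetectable LDL-C value, a range is determined".

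The floor is also tied to that analysis: "In the sensitivity analysis, imputed baseline values will be restricted to" at least 0.1, "to avoid imputed values close to zero which can lead to numerical instabilities in the analysis of percentage LDL-C change from baseline".

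**The concern.** An undetectable value is censored, which is more informative than missing: it is known to lie in an interval. An unrestricted MAR draw ignores the interval. Two consequences follow.

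- **Post-baseline values.** If LDL-C is undetectable because total cholesterol (TC) is low, the affected values concentrate in the inclisiran arms. MAR draws replace them with values typical of detected patients, which understates the effect. If low triglycerides (TG) are the cause, there is little bias but some loss of precision.
- **Baseline values.** Baseline is the divisor of the endpoint (SAP 2.1.1). The SAP itself names the hazard of imputed baselines near zero, but guards against it only in the sensitivity analysis.

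The size of the difference is the estimand's summary measure (SAP 2.5.1), so the estimate and its interval matter even when the test is safe.

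**Working it through.** **The plan's own figures.** For an effect size of 0.3, 90% power and one-sided 0.025: n = 2 × (1.960 + 1.282)² / 0.3² = 233.5, so 234. With 20% drop-out, 234 / 0.8 = 292.5, so 293, against 300 stated: reproduced. For LDL-C (SD 30 and 20), SE = √((30² + 20²)/300) = 2.08, so the 95% half-width is 1.96 × 2.08 = 4.1 points. Power for 10 points is Φ(10/2.08 − 1.96) = 99.8%. The documents state no figure for the undetectable-value rule.

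**Inputs from the documents.** Baseline LDL-C 2.7 mmol/L (Protocol 1.1.4.1); reduction about 50% (Protocol 1.1.4); SDs as above (Protocol 12.8, SAP 3); TC at least 4 at entry (Protocol 5.1), but read from the medical record (Protocol 8.2), so device TC at baseline may be lower; LDL-C = TC − HDL − TG/2.2 (SAP 2.5.4); 500 imputations (SAP 2.5.2).

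**Assumed.** Control change 0; baseline SD 0.9, values above 0.6; HDL 1.3 (SD 0.35); TG median 1.4 (log SD 0.45); between-visit correlation 0.8 for HDL and 0.6 for TG; Day 90 to Day 270 correlation of change 0.3 and 0.6 (0.45 in the 300-per-arm runs); no drop-out. Device limits were set so that 5% or 10% of inclisiran Day 270 values are undetectable, with the same limits in control. Imputation was multivariate normal by arm, unrestricted or truncated to the range, followed by unequal-variance ANCOVA and Rubin's rules.

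**Bias of the treatment difference toward no effect, in points** (40,000 per arm, baselines taken as detectable):

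| Share of undetectable values due to low TC | 5% undetectable | 10% undetectable |
|---|---|---|
| All | 0.9 to 1.3 | 1.6 to 2.4 |
| Half | 0.5 to 0.7 | 0.8 to 1.2 |
| A quarter | 0.2 to 0.3 | 0.4 to 0.6 |
| None (TG only) | under 0.1 | under 0.1 |

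With draws held to the range, bias is about 0.1 or less throughout. Of the unrestricted Day 270 draws, 66-87% fall outside their own range. A further check of the TC-only case gave 1.2-1.3 and 2.1-2.5 points, with 60-79% of draws out of range. There, bounded draws left 0.05-0.6 points when the model was fitted to detected values only.

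A separate simulation used a plain LDL-C cut-off (baseline mean 2.9, SD 0.8; within-patient correlation 0.7). With 7% undetectable, the unrestricted estimate was −47.5 against a true −49.5, a bias of 2.0 points; bounded draws gave −49.5. With 40% it was −39.8 against −49.7; bounded draws gave −50.2.

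**Coverage of the 95% interval, TC only, 300 per arm.** Simulated: 90-94% at 5% and 80-87% at 10%, against 95-96% bounded (Monte Carlo SE 1-1.6 points). As a check at 10%, coverage is about Φ(1.96 − b/SE) − Φ(−1.96 − b/SE). Midpoint biases are b = (2.37 + 2.12)/2 = 2.245 with TC of at least 4 enforced on the device, and (1.87 + 1.62)/2 = 1.745 without. With SE 2.08 these give 81% and 87%.

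**Baselines near zero.** An imputed baseline of 0.05 with a Day 270 value of 1.3 gives 100 × (1.3 − 0.05)/0.05 = +2500%. Against a typical −50%, one such patient among 300 moves the arm mean by (2500 + 50)/300 = 8.5 points in that imputed dataset. A draw of −0.05 gives −2700% and moves it by (−2700 + 50)/300 = −8.8.

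95% half-widths with TG as sole cause and no floor (51-67 simulated trials per setting, 500 imputations), device TC not limited to at least 4:

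| Undetectable | Median (90th percentile), no floor | Median, floor only | Median, bounded |
|---|---|---|---|
| 2% | 4.3 (7.4) | 4.2 | 4.0-4.1 |
| 5% | 4.8 (9.6) | 4.4 | 4.0-4.1 |
| 10% | 8.7 (35.8) | 4.8 | 4.0-4.1 |

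The bounded 90th percentile is 4.2. If device TC is also at least 4 at baseline, the 10% case falls to 4.4 (largest 7.0), against 4.1 bounded.

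**The case against.** The strongest reply is that the SAP already pre-specifies the range-based imputation, with the floor, the same washout rule and the same ANCOVA. The dispute would then be only about which analysis comes first. MAR is not the difference either, since both analyses assume it for undetectable values. This is fair as far as it goes, but the sensitivity analysis leaves the primary estimate unchanged. It also alters the range, the floor and the whole model at once, so a shift could not be traced to the range.

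Second, the public text breaks off at the end of 5.5.1, before the table on range determination, and a bound could sit there. That cannot be excluded. But SAP 2.5.5 describes use of the range as a change from the primary method, which makes a range bound in the primary unlikely.

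Third, the mechanism is not legible. The simulations cover low TC and low TG only; HDL or an upper device limit could act differently. The two harms also do not peak together: TC as sole cause gives 0-0.4% undetectable baselines, and TG as sole cause gives almost no bias. All of this stands, so each figure above is a single-cause illustration.

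Fourth, the largest bias is conservative and smaller than the interval's half-width, and drop-out would soften the coverage loss. At 240 per arm, SE = √(1300/240) = 2.33, and the formula above gives 84% and 88% instead of 81% and 87%. The softening is real but small.

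**Conclusion.** The concern holds on the legible text. The primary analysis discards information that the SAP says it can calculate, and leaves the endpoint's divisor unprotected against a hazard the SAP itself names.

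Superiority is not in doubt. What is exposed is the reported effect, by up to 2.4 points toward no effect in the main simulations at 10% undetectable, and the interval, through under-coverage or widening. If low TG is the only cause, bias is negligible and only precision suffers.

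All sizes depend on assumed undetectable fractions, device limits and lipid distributions, so confidence in the magnitude is moderate. The change should be made because it is inexpensive, not because the trial's main conclusion depends on it.

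**What to change.** 1. Keep the primary washout and MAR structure, and the imputation for drop-outs, as they are.
2. Treat undetectable values as interval-censored in the primary analysis: draw each one (baseline, Day 90, Day 270) within its calculated range. Preferably fit the imputation model to the censored values as well, since fitting to detected values alone can leave some bias.
3. Apply the 0.1 floor to imputed baselines in the primary analysis too. The floor alone brings the 10% TG-only median half-width from 8.7 to 4.8; the range brings it to about 4.1.
4. Keep the unrestricted MAR version and the Bayesian range-based model as sensitivity analyses.
5. Report undetectable counts by arm, visit and out-of-range lipid.
6. Correct the cross-reference: SAP 2.5.4 sends the sensitivity imputation to Appendix 5.5.1, while 2.5.5 and the table of contents place it in 5.5.2.

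If the unseen text already sets a bound and floor for the primary analysis, the sponsor need only confirm this and make changes 5 and 6.

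The cost is a SAP edit and additional imputation code. Value-specific bounds go beyond the PROC MI step described, but the ranges and R code must be produced for the sensitivity analysis anyway. No new data are needed, and the Bayesian model and its priors are not imposed on the primary analysis.

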#### 2.10.1 Other efficacy data

A capillary blood sample will be taken for immediate analysis of the participants lipid profile for assessment of efficacy. This will be performed at screening/baseline visit, day 90 visit and EOS (day 270) visit in the following:

• LDL-C calculated using Friedwald

Descriptive summaries by treatment group will be presented.

Line-Plot displaying mean and SE of change from baseline will be provided for all parameters using all available visits.

Descriptive summaries by treatment group will be presented.

Listing of all above endpoints for all available visits will be provided.

The threshold analysis on LDL-C data will be performed. Frequency and percentage of patients with secondary prevention who achieved following threshold targets at day 270 will be provided.

- <1.8 mmol/L (<70 mg/dL)
- <1.4 mmol/L (<55 mg/dL)

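### The primary analysis imputes undetectable LDL-C readings under MAR and ignores the range that the SAP itself derives for them; if low total cholesterol is the cause, the inclisiran effect is understated.

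*SAP*

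**What the plan says.** Lipids are measured on a point-of-care device, and LDL-C is calculated by Friedewald's formula as total cholesterol minus HDL minus triglycerides/2.2 (SAP 2.5.4). For the primary analysis: "Any undetectable calculated LDL-C data due to device sensitivity for a lipid parameter will be considered as missing for the primary analysis".

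Appendix 5.5.1 says how these gaps are filled. Values undetectable "due to device sensitivity for a lipid parameter in inclisiran groups will be considered as missing and imputed under MAR assumption"; control-arm undetectables are also MAR. The predictors are LDL-C values only, for example "Observed value of efficacy measurement at Day 90 (continuous)". The washout branch leaves these readings out: it is for "For the subjects in the inclisiran groups and with missing data at Day 270 which does not includes undetectable data". No detection-limit information enters the primary imputation.

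SAP 2.5.5 takes a different view in a sensitivity analysis. It says that undetectable values provide information and that "a range for an LDL-C value can be calculated"; "In this sensitivity analysis, the LDL-C range is considered in the imputation model". The appendix text on this method, which the table of contents lists as 5.5.2, says: "For each undetectable LDL-C value, a range is determined based on" Friedewald's formula. The other sensitivity analysis, an MMRM without imputation, uses no range.

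SAP 2.10.1 adds a descriptive table at <1.8 and <1.4 mmol/L: "Frequency and percentage of patients with secondary prevention who achieved following threshold targets at day 270 will be provided". The visible text gives no rule for an undetectable Day 270 value.

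**The concern.** A value lost because a measured lipid fell outside the device's limits is known to lie in an interval. MAR imputation from readable values ignores that interval and can place the value where it could not have been. Inclisiran lowers LDL-C, and so total cholesterol. If the lower total-cholesterol limit is the one that matters, undetectable readings gather among good responders on inclisiran and are replaced by more ordinary responses.

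At stake are the estimated percentage change, its confidence interval and the proportions reaching target, which are the figures a health service would carry forward from an implementation trial.

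**Working it through.** **The plan's own figures.** The SAP gives no expected number or effect of undetectable readings. Its LDL-C power statement holds. With SDs of 30% and 20% and 300 × 0.8 = 240 evaluable per arm, power for a 10-point difference is 99.0% at one-sided 0.025 and 98.0% at 0.0125, the first Holm step.

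**What a range looks like.** Assume HDL 1.3 and triglycerides 1.5 mmol/L.
- Total cholesterol below 2.6: LDL-C < 2.6 - 1.3 - 1.5/2.2 = 0.62 mmol/L. Limits of 2.3 and 2.0 give 0.32 and 0.02.
- Only triglycerides undetectable, below an assumed 0.8: LDL-C is known to within 0.8/2.2 = 0.36 mmol/L of total cholesterol minus HDL.

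In the first case MAR imputes about 1.4-1.5 mmol/L, well above the possible range. In the second it discards a nearly known value.

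**Simulation inputs.** From the documents: change of -50% to -55% (Protocol 1.1.4), SD 20% on inclisiran (SAP 3), entry total cholesterol ≥4 mmol/L (Protocol 5.1), and Friedewald's formula. Assumed: baseline LDL-C 2.8 (SD 0.8) before the entry filter, against 2.7 in the two earlier ASCVD trials; HDL about 1.3; median triglycerides 1.5; HDL and triglycerides unaffected by treatment; Day 90/Day 270 correlation 0.6; a lower total-cholesterol limit of 2.0 to 2.6. Undetectable values are imputed by regression on baseline and Day 90 with random residuals.

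| Assumed limit (mmol/L) | Undetectable at Day 270 | Understatement, true change -50% |
|---|---|---|
| 2.0 | about 1% | 0.4 points |
| 2.3 | about 3% | 1.1 points |
| 2.6 | about 8% | 2.4 points |

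At -55% and limit 2.6 the understatement is about 3.2 points. Taking baseline SD 0.9, correlations of 0.3 to 0.8 and changes of -50% to -55% gives 0.2-0.5, 0.9-1.5 and 2.1-3.4 points at the three limits. The limit governs the size: at 2.9 the same calculation gives 4.3-6.0.

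**Arithmetic check.** Bias = share undetectable × (imputed mean - true mean in that group). At -50%, limit 2.6, correlation 0.8 and SD 0.9: 0.076 × (-52.4 + 80.5) = 2.1, matching the arm mean moving from -49.9 to -47.8. The SD in that run shrinks from 19.8 to 18.3.

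**Effect on the interval.** SE of the difference = √(30²/240 + 20²/240) = 2.33 points. A bias of 2.4 is 1.03 SE, so a nominal 95% interval covers Φ(1.96 - 1.03) - Φ(-1.96 - 1.03) = 82%. At 3.2 points (1.37 SE) it covers about 72%; at 0.4 (0.17 SE), about 95%.

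**Targets.** At limit 2.6 and -50%, the share <1.4 mmol/L falls from 47% to about 43% with imputed values, 42% with undetectables omitted, or 39% with them counted as not achieved.

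**Other causes.** With undetectability from low triglycerides (assumed limits 0.5-0.8), high HDL (>2.0; about 6% of values) or low HDL (<0.8; 2.5%), the bias in the mean is about 0.01 points or less, and the imputed share <1.4 moves by no more than a few tenths of a point. The threshold table can still suffer: if 6% are undetectable regardless of LDL-C and are counted as failures, 47% becomes 0.47 × 0.94 = 44%.

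**The case against.** The strongest reply is that the mechanism is not established. The sentence in SAP 2.5.5 naming the lipids is cut in the public copy, and a value outside a limit need not be below it. Appendix 5.5.1 also provides for undetectable baseline values, which a low total-cholesterol limit would hardly produce in people entered at ≥4 mmol/L. That suggests other causes, though not conclusively, because Protocol 8.2 takes entry total cholesterol from the medical record and not from the device. This objection stands. A reader might infer that the device loses the strongest responders and that the effect is therefore understated; the documents support that only conditionally.

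Second, the range-based analysis is already pre-specified with 500 datasets and the primary ANCOVA, and the primary choice is conservative for superiority. That limits the harm. But it leaves the headline estimate on the weaker assumption, and it covers only the mean change, not the threshold table.

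Third, simply exchanging the two analyses would bring the normal model for undetectable baselines, the 0.1 floor and the Bayesian priors into the primary analysis. This is correct, and the change should be narrower than a swap.

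Fourth, SAP 2.10.1 does not say whether the table uses observed or imputed values, the surrounding text is partly removed, and the table is descriptive and limited to secondary prevention, whereas the simulation covers all participants. The attainment figures are therefore illustrations of possible readings.

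**Conclusion.** The point holds in a conditional form. The primary rule treats censored readings as ordinary missing data and leaves out information that the SAP says it has; this does not depend on the hidden limits. The size does. Over assumed total-cholesterol limits of 2.0 to 2.6 mmol/L, with low total cholesterol as the cause, the inclisiran reduction is understated by about 0.4 to 2.4 points at -50%, and by up to about 3.2 at -55%. With low triglycerides or high HDL as the cause, the bias in the mean is negligible.

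A reader might also infer that the superiority conclusion is at risk. It is not. The bias runs against inclisiran, and with a control change near zero a difference of 50 - 2.4 = 47.6 points is still about 20 SE. What is exposed is the effect estimate, the coverage of its interval and the attainment rates.

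**What to change.** - **Primary imputation (SAP 2.5.4, Appendix 5.5.1):** confine draws for undetectable post-baseline LDL-C to the range implied by the device limits and Friedewald's formula. Leave other missing data and undetectable baselines as they are.
- **Sensitivity analysis:** keep the unconstrained MAR treatment of undetectables here.
- **Appendix text on undetectable data, step 2:** it draws from the posterior predictive distribution without saying that the draw must fall in the range. Say so.
- **SAP 2.10.1:** count an undetectable Day 270 value as below a target when the upper end of its range is below that target. State how the remaining undetectables are treated.
- **Reporting:** give the number of undetectable readings by arm, visit and lipid, so that a reader can see which mechanism applies.
- **Cross-reference:** SAP 2.5.4 sends the undetectable-value sensitivity imputation to Appendix 5.5.1; it should point to 5.5.2, as 2.5.5 does.

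The cost is SAP wording and a somewhat more complex primary imputation program. The ranges are already to be derived, and no new data are needed.
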